## 9.2 Statistical Evaluation of Dose Proportionality and Food Effect

A dose-normalized plot will be produced to investigate the dose proportionality of  $AUC_{last}$ ,  $AUC_{24}$ ,  $AUC_{inf}$  and  $C_{max}$  for Part A and Part B (Day 1 and Day 14). A statistical analysis will be conducted to investigate the food effect on the treatment by comparing Test treatment (fed) to Reference treatment (fasted).

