4.1.1. Single Ascending Dose and Food Effect- Part A

4.1.1.1. Single Ascending Dose (Cohorts 1 and 2)

Dose escalation will proceed according to a double-blind (investigator and participant), 4-period crossover, single ascending dose methodology. Up to 2 cohorts of participants will be evaluated.

Cohorts 1 and 2 will be dosed in a sequential manner for up to 4 periods each (see schema in Section 1.2). Progression to each dose level will occur following evaluation of all available cumulative safety, tolerability, PK, and other emergent data from the previous cohorts and periods.

The current trial may evaluate up to 8 different dose levels in Cohorts 1 and 2; however, some doses may be repeated, if required. The starting dose for Part A will be 0.5 mg. Doses, in general, will be escalated in Cohort 1 and Cohort 2 until the maximum tolerated dose is achieved or the CVL-354 exposures (C_{max} and AUC₂₄) reach, or are projected to reach, the predefined human exposure limits

Dose escalation may also be stopped if it is determined that sufficient exposures are achieved, based on estimated target occupancy. The proposed doses in Part A for Cohorts 1 and 2 are presented in Table 8. Based on emergent data, the actual doses may change (from those presented in Table 8); however, new doses will not exceed half-log increments (3.3-fold) from previous dose. Smaller increments (eg, ≤2-fold) will be evaluated as exposures approach the proposed stopping criteria. All dosing decisions will be made jointly by the sponsor and the investigator after review of all available safety, tolerability (through 72 hours postdose), and PK data (through 24 hours postdose) at an SRT meeting.

Actual doses administered to Cohorts 1 and 2 at the time of the protocol amendment (Version 3.0) are provided in Section 2.2.5.

Table 8: Example Dosing Paradigms for CVL-354 Single Ascending Dose in Cohorts 1 and 2

Cohort	N	Period 1	Period 2	Period 3	Period 4
Cohort 1	2	Placebo	1.5 mg	5 mg	10 mg
	2	0.5 mg	Placebo	5 mg	10 mg
	2	0.5 mg	1.5 mg	Placebo	10 mg
	2	0.5 mg	1.5 mg	5 mg	Placebo
Cohort 2	2	Placebo	40 mg	80 mg	100 mg
	2	20 mg	Placebo	80 mg	100 mg
	2	20 mg	40 mg	Placebo	100 mg
	2	20 mg	40 mg	80 mg	Placebo

Doses/treatment may be modified based on emergent safety, tolerability, and pharmacokinetic data. Doses may be repeated to confirm safety/tolerability.

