During dose escalation, Cohorts 1 and 2 will employ sentinel dosing (n=2; 1 CVL-354 and 1 placebo) during each period to ensure safety and tolerability before proceeding to dosing of non-sentinel participants for that period. The investigator will review AEs (serious and

nonserious) and all available safety data from the first 24 hours after dosing for the 2 sentinel participants. If clinically significant safety concerns are observed in sentinel participants, dosing of the rest of the cohort will be paused in order for the SRT to discuss the findings and determine subsequent actions. If no safety concerns are observed in the sentinel participants, the investigator will provide written documentation for sponsor confirmation before proceeding to dosing of non-sentinel participants.

Check-in assessments conducted on Day -1 of each period will include both sentinel and non-sentinel participants. No additional check-in assessments will be required for non-sentinel participants prior to dosing if the Check-in assessments are performed within 48 hours prior to dosing.

Each dosing period for the dose escalation portion of Part A will be separated by a washout period of at least 5 days (ie, administration of subsequent doses of investigational medicinal product [IMP] will not occur until at least 5 days after the previous dose of IMP).

Cohorts 1 and 2 will comprise approximately 8 participants each (3:1 ratio of CVL-354 to placebo within each treatment period). All participants will receive single oral doses of CVL-354 or placebo during each period. All doses during dose escalation will be administered under fasted conditions following a 10-hour overnight fast. Participants will continue to fast for 4 hours following dosing on Day 1.

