6.1. Trial Treatments Administered

A summary of the IMP to be administered during this trial is presented in Table 10.

Table 10: Investigational Medicinal Product Administered

IMP	CVL-354 Solution (Extemporaneous)	CVL-354 Capsules	Placebo	
Туре	Drug	Drug	Drug	
Dose Formulation	Oral solution	Capsule	Matching oral solution vehicle (without active pharmaceutical ingredient) Matching capsule filled with silicified microcrystalline cellulose	
Unit Dose Strength(s)	0.5 mg/10 mL – 500 mg/10 mL	5 mg, 25 mg, 100 mg	Not applicable	
Dosage	Part A Cohort 1	Part A Cohort 3	Not applicable	
Level(s)	0.5, 1.5 mg, 5 mg, or 15 mg	50 mg		
	Part A Cohort 2	Part B Cohorts 2-5		
	45 mg, 90 mg, 150 mg, or 200 mg	25 mg QD, 50 mg QD, 100 mg QD, or 150 mg QD		
	Part B Cohort 1			
	10 mg QD			
Route of Administration	Oral	Oral	Oral	
Sourcing	CVL-354 capsules will be provided by Cerevel. The CVL-354 oral solution preparation will be supplied by Cerevel and the solution will be prepared by the pharmacy of the trial site.			
Packaging and Labeling	Capsule IMP provided by Cerevel will be in 60 cc HDPE bottles and should be stored in accordance with the drug label.			
	The CVL-354 API for oral solution provided by Cerevel and oral solution will be supplied in amber-glass bottles. The bottles will be labeled according to local regulatory requirements and language. Oral solution will be prepared before dosing by the pharmacy of the trial site.			

Abbreviations: API=active pharmaceutical ingredient; HDPE=high-density polyethylene; IMP=investigational medicinal product; QD=once daily.

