### 1.1.3. Part B (Multiple Ascending Dose)

The safety and PK of double-blind (investigator and participant), multiple-dose administration of CVL-354 will be evaluated in Part B of the trial after completion of dose escalation in Part A. Part B may overlap with Part A Cohort 3 (evaluation of food effect on CVL-354 exposures).

Up to 5 sequential cohorts of 10 participants each will be evaluated in Part B. Participants will receive oral doses of either CVL-354 or placebo for up to 14 days. Eligible participants will be admitted to the clinic on Day -1 and will be randomized in a 4:1 ratio (8 participants active treatment: 2 participants placebo). Cohorts will be initiated in a sequential manner after review of all available safety, tolerability, and PK data (at least up to Day 15) from previous cohorts.

Each dose of CVL-354 will be administered once daily (QD) throughout Part B of the trial based on data obtained during Part A of the trial.

The starting dose for Part B will be 10 mg QD. In Part A, a single oral CVL-354 dose of 200 mg was deemed to be safe and well tolerated. The exposures from daily doses of 10 mg QD are expected to be well below the highest exposures investigated in the SAD part [REDACTED]

[figure not shown]
[REDACTED] Only the 10 mg QD dose will be administered as an extemporaneously prepared solution (same formulation as Part A) in Part B. All other subsequent doses will be

administered as capsule. During Part B, all preceding doses should be deemed safe and tolerated before progressing to higher doses. Similar to Part A, dose increments in Part B will not exceed half-log increments (3.3-fold) early in escalation and smaller escalation steps ( $\leq 2$ -fold) will be implemented at doses closer to stopping criteria. Standard safety laboratory assessments, vital sign measurements, safety electrocardiograms (ECGs), and AE data will provide the relevant safety data up to Day 17 to make the dose-escalation decision. Furthermore, dose-escalation decisions will be made by the SRT.

On days with intensive PK sampling (Days 1 and 14), IMP will be administered under fasted conditions following a 10-hour overnight fast. Participants will continue to fast for 4 hours following dosing on these intensive PK sampling days. On other days, each dose of IMP will be administered at approximately the same time each morning at least 1 hour following the morning meal. Each dose of IMP will be administered orally with approximately 240 mL of water.

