### List of Tables, Figures, and Listings

Table 14.2.1.1a Summary of Pharmacokinetic Concentrations (Pharmacokinetic Analysis Set)  
Part A

Table 14.2.1.1b Summary of Pharmacokinetic Concentrations (Pharmacokinetic Analysis Set)  
Part B

Table 14.2.1.2a Summary of Pharmacokinetic Parameters (Pharmacokinetic Analysis Set) Part A

Table 14.2.1.2b Summary of Pharmacokinetic Parameters (Pharmacokinetic Analysis Set) Part B

Table 14.2.1.3 Summary of Pharmacokinetic Excretion Parameters by Time Interval  
(Pharmacokinetic Analysis Set) Part B

Table 14.2.1.4 Summary of Pharmacokinetic Cumulative Excretion Parameters by Time Interval  
(Pharmacokinetic Analysis Set) Part B

Table 14.2.1.5 Statistical Analysis of Pharmacokinetic Parameters (Food Effect Assessment)  
(Pharmacokinetic Analysis Set)

Figure 14.2.1.1a Arithmetic Mean ( $\pm$ SD) Pharmacokinetic Concentration-time Profiles  
(Pharmacokinetic Analysis Set) Part A

Figure 14.2.1.1b Arithmetic Mean ( $\pm$ SD) Pharmacokinetic Concentration-time Profiles  
(Pharmacokinetic Analysis Set) Part B

Figure 14.2.1.2a Overlaying Individual Pharmacokinetic Concentration-time Profiles  
(Pharmacokinetic Analysis Set) Part A

Figure 14.2.1.2b Overlaying Individual Pharmacokinetic Concentration-time Profiles  
(Pharmacokinetic Analysis Set) Part B

Figure 14.2.1.3 Overlaying Individual Pharmacokinetic Concentration-time Profiles Across All  
Days (Pharmacokinetic Analysis Set) Part B

Figure 14.2.1.4a Boxplots of Dose-Normalized Pharmacokinetic Parameters (Pharmacokinetic  
Analysis Set) Part A

Figure 14.2.1.4b Boxplots of Dose-Normalized Pharmacokinetic Parameters (Pharmacokinetic  
Analysis Set) Part B (Day 1 and Day 14)

Listing 16.2.6.1.1 Pharmacokinetic Blood Collections (Safety Analysis Set)

Listing 16.2.6.1.2 Pharmacokinetic Urine Collections (Safety Analysis Set)

Listing 16.2.6.1.3 Pharmacokinetic Concentrations (Safety Analysis Set)

Listing 16.2.6.1.4 Pharmacokinetic Parameters (Safety Analysis Set)

Listing 16.2.6.1.5 Regression Analysis Data for the Apparent Terminal Elimination Phase  
(Safety Analysis Set)

Listing 16.2.6.1.6 Pharmacokinetic Excretion Parameters by Time Interval  
(Safety Analysis Set)

Listing 16.2.6.1.7 Pharmacokinetic Cumulative Excretion Parameters by Time Interval  
(Safety Analysis Set)

Figure 16.2.6.1a Individual Pharmacokinetic Concentration-time Profiles (Safety Analysis Set)  
Part A

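### Part A dose proportionality is shown only by boxplots and by-dose summaries, which give no slope or interval and leave the crossover pairing unused

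*SAP*

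**What the plan says.** PKAP 9.2 covers both dose proportionality and food effect.

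- **Dose proportionality.** The whole method is one sentence: "A dose-normalized plot will be produced to investigate the dose proportionality", for AUClast, AUC24, AUCinf and Cmax in Parts A and B. PKAP section 13 gives the form for Part A as "Figure 14.2.1.4a Boxplots of Dose-Normalized Pharmacokinetic Parameters", with a matching Part B figure. No model, slope, interval or criterion is stated. Dose-normalized parameters are also derived for each profile (PKAP 8.1), and PKAP 9.1 has all PK parameters summarized by treatment and listed individually.
- **Food effect.** The same section fits a mixed model with participant as a random effect and reports 90% CIs.
- **Design.** Protocol 4.1.1.1 describes a "4-period crossover, single ascending dose methodology" with about 8 participants per cohort and a 3:1 active-to-placebo ratio in each period. Protocol Table 10 gives Cohort 1 doses as "0.5, 1.5 mg, 5 mg, or 15 mg" and Cohort 2 doses as "45 mg, 90 mg, 150 mg, or 200 mg".
- **Part B.** SAP 1.1.3 states "Only the 10 mg QD dose will be administered as an extemporaneously prepared solution". All later doses are capsules.

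**The concern.** Each SAD participant is planned to contribute three active profiles, so most of the information on how exposure scales with dose lies in comparisons within a participant. A box per dose spreads those profiles over separate groups. Box width then combines between- and within-participant variation, although the first largely cancels when the same people are compared across doses. A reader can miss a real departure inside a cohort and has no interval showing how large a departure the data could exclude.

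Between cohorts the difficulty is different. Going from 15 mg to 45 mg changes every participant as well as the dose. A chance difference between two groups of eight can look like non-proportionality, or can mask it.

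What is at stake is the PK interpretation in the study report. Protocol 4.2, for example, says that a food effect at 50 mg may be extrapolated to lower doses. Readers will want a slope and its precision when they weigh statements of that kind.

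**Working it through.** The documents state no precision, power or criterion for dose proportionality, so there is no figure to reproduce. The check compares the SE of the log-log slope under different uses of the same data.

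**Inputs from the documents.** The sequence layout is that of Protocol Table 8: four sequences of two participants, each omitting one dose for placebo. This gives 6 active profiles per dose, 24 per cohort and 48 in all. Two doses in a cohort share 8 - 2 - 2 = 4 recipients. Doses are from Protocol Table 10.

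**Assumptions.** The CVs are assumed, with log-scale variances σ² = ln(1 + CV²). Variances are treated as known.

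**Formulas, one cohort.** Let S be the sum of squares of ln(dose) about its mean over the 24 profiles. Because each participant omits one of four doses, 8/9 of S lies within participants and 1/9 between them, whatever the doses are.

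- Read as independent: SE² = (σb² + σw²)/S
- Actual SE of an unpaired slope, since the shared participants cancel in part: SE² = (σw² + σb²/3)/S
- Participant random effect: SE² = 1/{S × [8/(9σw²) + 1/(9(σw² + 3σb²))]}

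**Cohort 2 at 40%/20%.** The ln(dose) values are 3.807, 4.500, 5.011 and 5.298. Their squared deviations sum to 1.284, so S = 6 × 1.284 = 7.70. Also σb² = ln 1.16 = 0.1484 and σw² = ln 1.04 = 0.0392.

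- Independent: √(0.1876/7.70) = 0.156
- Unpaired, actual: √(0.0887/7.70) = 0.107
- Participant effect: 1/√(7.70 × 22.89) = 0.075

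| CV between/within | Independent | Unpaired, actual | Participant effect | Independent ÷ participant | Unpaired ÷ participant |
|---|---|---|---|---|---|
| 30%/30% | 0.150 | 0.122 | 0.110 | 1.35 | 1.11 |
| 30%/20% | 0.128 | 0.094 | 0.075 | 1.70 | 1.25 |
| 40%/20% | 0.156 | 0.107 | 0.075 | 2.07 | 1.42 |
| 50%/20% | 0.185 | 0.121 | 0.075 | 2.45 | 1.61 |
| 20%/25% (unfavourable case) | 0.114 | 0.098 | 0.092 | 1.24 | 1.06 |

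SEs are for Cohort 2. The ratios are the same in Cohort 1, because S cancels.

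**What this means on the exposure scale.** Cohort 2 spans ln(200/45) = 1.492. At 40%/20%, a 90% CI (1.645 × SE) resolves a departure across that range to a factor of exp(1.645 × 0.075 × 1.492) = 1.20 with the participant effect. The factor is 1.30 for an unpaired slope and 1.47 when profiles are read as independent.

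**The 15-to-45 mg step.** No participant is shared, so the contrast has SE = √(2(σb² + σw²)/6), which is 0.250 at 40%/20%. Under exact proportionality, the chance of an apparent step of 1.3-fold or more in either direction is 2[1 - Φ(0.262/0.250)] = 29%, and 20-37% over the first four rows. A participant effect lowers the SE only to 0.226 and the chance to 17-32%.

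**Pooled slope.** At 40%/20% the SE is 0.027 without a cohort term and 0.031 with one. The cohort-adjusted slope rests mainly on Cohort 1, whose S is 39.05: 39.05/(39.05 + 7.70) = 84% of the information.

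**The case against.** The case for leaving the plan alone is substantial.

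- **Not an objective.** Dose proportionality is not among the objectives or endpoints and does not appear in Protocol 9.4.3. The food effect is a secondary objective with a model specified in the protocol, which explains why 9.2 treats the two differently. This stands, and it limits the priority.
- **No test is planned.** A reader might infer an inflated error rate. An ordinary regression that treated the 48 profiles as independent would reject exact proportionality in 20-29% of trials at a nominal 10%. The documents do not support that criticism: the PKAP plans no such regression, and both documents say that no formal hypothesis testing is planned. A boxplot rejects nothing.
- **Other outputs exist.** Dose-normalized parameters are also summarized by treatment and listed by participant, so the pairing can be recovered by hand. What is missing is a slope, an interval and a display that uses the pairing.
- **Escalation.** A reader might infer that this figure drives the PK stopping rules. PKAP 10.1 bases the interim PK analyses that support escalation on group summaries, and nothing links the 9.2 figure to them. SAD escalation was already complete at protocol version 3.0.
- **Layout unseen.** Figure shells are in a separate document. Participant lines, cohort panels or formulation labels may be there, although the PKAP does not require them.

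**Conclusion.** The point holds as a matter of efficiency and interpretation. The planned output gives no slope or interval and does not use the crossover pairing. With assumed CVs of 30-50% between and 20-30% within participants, the within-cohort slope SE is about 1.35 to 2.45 times larger when profiles are read as independent than with a participant effect. Part of that is how the boxes read. Compared with the actual SE of an unpaired slope, the gain is 1.11 to 1.61 times, and it nearly vanishes (1.06) at 20%/25%. All of these figures rest on assumed CVs and known variances. With variances estimated from eight participants per cohort, the intervals would be somewhat wider.

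It would be too strong to say that the 15-to-45 mg step is purely a change of people. It is a 3-fold dose change confounded with cohort, and because no dose is shared, no model can fully separate the two. No planned test is invalid, and no primary endpoint or escalation rule is affected. Priority is optional to moderate.

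**What to change.** Add to PKAP 9.2, beside the boxplots:

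- For Part A Cohorts 1 and 2 only (fasted, solution), a descriptive power model: ln(parameter) = cohort + slope × ln(dose), with participant as a random effect, for Cmax, AUClast, AUC24 and AUCinf.
- As the main output, the slope and 90% CI within each cohort. Report a cohort-adjusted pooled slope as well. A pooled slope without the cohort term would absorb the cohort difference.
- On the Part A plot, lines joining each participant's dose-normalized values and a mark where the cohort changes.
- A statement that Cohort 3 (50 mg capsule, fed and fasted) is left out of both the model and this plot, since 9.2 says only Part A.
- A label on the Part B plot showing the 10 mg group as solution, because formulation and dose change together there.

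The cost is PKAP wording, a short mixed-model call per parameter and one extra table, all on data already collected. The cohort term raises the pooled-slope SE (0.031 against 0.027 at 40%/20%). A single slope may not fit the whole 400-fold range (0.5 to 200 mg), which is a further reason to lead with the within-cohort slopes. The 15-to-45 mg step stays confounded with cohort, and the report should say so.

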### For Food effect:

The ln-transformed  $AUC_{inf}$ ,  $AUC_{last}$ ,  $AUC_{24}$  and  $C_{max}$  for CVL-354 will be analyzed using a linear mixed model. The model will include planned treatment sequence, period, and actual treatment (i.e., fast/fed status) as fixed effects, and participant within planned treatment sequence as a random effect.

For each PK parameter separately, the least squares mean (LSM) for each treatment, difference in LSMS between the fed and fasted treatments, and corresponding 90% CI will be calculated; these values will then be back-transformed to give the GLSM, ratio of GLSMs, and corresponding 90%.

Additionally, the pooled estimate (across treatments) of the within-subject CV will be calculated, and residual plots will be produced to assess the adequacy of the model(s) fitted.

Examples of the SAS code that will be used are as follows:

### Mixed Model Analysis

```
proc mixed data = <data in>;
  by parcat1n parcat1 pkday paramn param;
  class trtan aperiod trtseqp usubjid;
  model lpk = trtan aperiod trtseqp / cl residual ddfm = kr2;
  lsmeans trtan / cl pdiff = control('1') alpha = 0.1;
  random intercept / subject = usubjid(trtseqp);
  ods output lsmeans = <data out>;
  ods output diff = <data out>;
  ods output covparms = <data out>;
run;
```

## 10 PHARMACOKINETIC REPORT

### 10.1 Interim PK Analyses

An interim PK analysis is planned for Part A after each period (1-4) for cohorts 1 and 2 to assess drug exposures. Cohort 3 of Part A will be used to study food effect. Part B will evaluate oral doses of either CVL-354 or placebo for up to 14 days that will be administered QD throughout Part B of the trial based on data obtained during Part A. The interim analysis consists of only group summary using descriptive statistics. Individual level data will be kept strictly confidential and will not be accessible to any study personnel except Bioanalytical laboratory personnel, Labcorp PK analysts, and Cerevel Clinical Pharmacology personnel pre-specified in the Cerevel Study Blind Protection Plan. It is critical to maintain the integrity of blind for the study. Additional interim PK analyses may be performed based on the results of the interim analyses. Interim PK reports will be completed after each interim analysis in support of dose escalation.

### 10.2 Final Report

The PK report for the analysis of CVL-354 in plasma and urine will contain a summary of the methodology, results, and conclusions. Prior to issuing a final report, Labcorp Clinical Pharmacology Services will provide the draft report to the Sponsor for review and comment. The report will include, but will not necessarily be limited to the following:

- Any changes from the planned analyses indicated in the PKAP
- The dates on which the study protocol are approved and the final report is issued

The report will be finalized after incorporation of Sponsor comments, as applicable. Unless otherwise specified, one electronic copy of the report will be sent to the Sponsor. The report will be finalized after approval from Sponsor or 6 months after issuing of draft report.

## 11 REGULATORY REQUIREMENTS

This pharmacokinetic analysis and report will be conducted in accordance with the protocol, this PKAP, Labcorp Standard Operating Procedures (SOPs), and other applicable regulatory requirements.

## 13 TABLES, FIGURES, AND LISTINGS

Shells are provided in a separate document to present examples of data presentation.

### List of Tables, Figures, and Listings

Table 14.2.1.1a Summary of Pharmacokinetic Concentrations (Pharmacokinetic Analysis Set)  
Part A

Table 14.2.1.1b Summary of Pharmacokinetic Concentrations (Pharmacokinetic Analysis Set)  
Part B

Table 14.2.1.2a Summary of Pharmacokinetic Parameters (Pharmacokinetic Analysis Set) Part A

Table 14.2.1.2b Summary of Pharmacokinetic Parameters (Pharmacokinetic Analysis Set) Part B

Table 14.2.1.3 Summary of Pharmacokinetic Excretion Parameters by Time Interval  
(Pharmacokinetic Analysis Set) Part B

Table 14.2.1.4 Summary of Pharmacokinetic Cumulative Excretion Parameters by Time Interval  
(Pharmacokinetic Analysis Set) Part B

Table 14.2.1.5 Statistical Analysis of Pharmacokinetic Parameters (Food Effect Assessment)  
(Pharmacokinetic Analysis Set)

Figure 14.2.1.1a Arithmetic Mean ( $\pm$ SD) Pharmacokinetic Concentration-time Profiles  
(Pharmacokinetic Analysis Set) Part A

Figure 14.2.1.1b Arithmetic Mean ( $\pm$ SD) Pharmacokinetic Concentration-time Profiles  
(Pharmacokinetic Analysis Set) Part B

Figure 14.2.1.2a Overlaying Individual Pharmacokinetic Concentration-time Profiles  
(Pharmacokinetic Analysis Set) Part A

Figure 14.2.1.2b Overlaying Individual Pharmacokinetic Concentration-time Profiles  
(Pharmacokinetic Analysis Set) Part B

Figure 14.2.1.3 Overlaying Individual Pharmacokinetic Concentration-time Profiles Across All  
Days (Pharmacokinetic Analysis Set) Part B

Figure 14.2.1.4a Boxplots of Dose-Normalized Pharmacokinetic Parameters (Pharmacokinetic  
Analysis Set) Part A

Figure 14.2.1.4b Boxplots of Dose-Normalized Pharmacokinetic Parameters (Pharmacokinetic  
Analysis Set) Part B (Day 1 and Day 14)

Listing 16.2.6.1.1 Pharmacokinetic Blood Collections (Safety Analysis Set)

Listing 16.2.6.1.2 Pharmacokinetic Urine Collections (Safety Analysis Set)

Listing 16.2.6.1.3 Pharmacokinetic Concentrations (Safety Analysis Set)

Listing 16.2.6.1.4 Pharmacokinetic Parameters (Safety Analysis Set)

Listing 16.2.6.1.5 Regression Analysis Data for the Apparent Terminal Elimination Phase  
(Safety Analysis Set)

Listing 16.2.6.1.6 Pharmacokinetic Excretion Parameters by Time Interval  
(Safety Analysis Set)

Listing 16.2.6.1.7 Pharmacokinetic Cumulative Excretion Parameters by Time Interval  
(Safety Analysis Set)

Figure 16.2.6.1a Individual Pharmacokinetic Concentration-time Profiles (Safety Analysis Set)  
Part A

Figure 16.2.6.1b Individual Pharmacokinetic Concentration-time Profiles (Safety Analysis Set)  
Part B
